### **13. ADVERSE EVENTS ANALYSIS, DEFINITION, AND REPORTING**

#### **13.1 Safety Analysis**

Safety will be analyzed for patients treated in this study.

At each visit, a brief focused history will be obtained and any indication of treatment related toxicity will be evaluated by appropriate examination and/or laboratory/radiographic studies.

Safety analyses will include summaries of adverse event rates and changes in laboratory results, as well as number of CTCAE toxicity grades for both laboratory and non-laboratory data.

The evaluation period should extend from date of first treatment until at least 30 days (or longer if so specified) from the last dose or until resolution from all acute toxicities associated with the drug administration.

#### **13.2 Definition of Adverse Event Terms**

**Adverse Event** – Any unfavorable and unintended sign (including an abnormal laboratory finding), symptom, or disease temporally associated with the use of a medical treatment or procedure regardless of whether it is considered related to the medical treatment or procedure (attribution of unrelated, unlikely, possible, probable, or definite, per NCI – CTEP).

**Serious Adverse Event (SAE)** – Any adverse drug experience occurring at any dose that results in any of the following outcomes:

- death,
- a life-threatening adverse drug experience,
- in patient hospitalization or prolongation of existing hospitalization,
- any persistent or significant disability/incapacity,
- or a congenital anomaly/birth defect.

Important medical events that may not result in death, be life-threatening, or require hospitalization may be considered a serious adverse drug experience when, based upon appropriate medical judgment, they may jeopardize the patient or subject and may require medical or surgical intervention to prevent one of the outcomes listed in this definition.

**“Serious” Versus “Severe” Adverse Events** – There is a distinction between serious and severe AEs. Assessment of seriousness will be made solely by the serious criteria listed above. Severity of AEs will be graded according to the NCI Common Terminology Criteria for Adverse Events v3.0. Therefore, serious events will not be automatically considered severe. For example, a stroke that results in only a limited degree of disability may be considered a mild (not severe) stroke, but it would still meet serious criteria and thus, be captured as an SAE. Similarly, severe events may not always be serious. An example would be an episode of severe, transient nausea which persists for several hours. This would be classified as a “severe” episode of nausea, but if it did not require treatment, intervention, or somehow meet other serious criteria, it would not be considered an SAE.

**Life-threatening Adverse Drug Experience** – Any adverse drug experience that places the patient or subject, in the view of the investigator, at immediate risk of death from the reaction as it occurred, i.e. it does not include a reaction that, had it occurred in a more severe form, might have caused death.

**Unexpected Adverse Drug Experience** – Any adverse drug experience, the specificity or severity of which is not consistent with the current investigator brochure; or, if an investigator brochure is not required or available, the specificity or severity of which is not consistent with the risk information described in the general investigational plan. “Unexpected” as used in this definition, refers to an adverse drug experience that has not been previously observed (e.g., included in the investigator brochure) rather than from the perspective of such experience not being anticipated from the pharmacological properties of the pharmaceutical product.

### **13.3 Toxicity Grading**

Toxicities will be graded according to the current version of the NCI Common Terminology Criteria for Adverse Events (CTCAE) Version 4.0. The full text of the NCI CTCAE is available online at: <http://ctep.cancer.gov/>

If a certain event or symptom is not described in the CTCAE grades, use the following grading scale:

- Mild: awareness of event but easily tolerated
- Moderate: discomfort enough to cause some interference with usual activity
- Severe: inability to carry out usual activity
- Very Severe: debilitating, significantly incapacitates patient despite symptomatic therapy

### **13.4 Toxicity Attribution**

Assessment of attribution is made by consideration of all clinically relevant data prior to, during, and after occurrence of the event, including diagnostic tests to assess the cause of the event. Clinically relevant data include, but are not limited to; underlying disease, past and present medical history (all concurrent non-malignant disease), concurrent medications, and timing between event and drug administration. The mechanism of action and prior toxicology of the study drug should be considered.

An adverse event is associated with the use of the drug when there is a reasonable possibility that the experience may have been caused by the drug.

Attribution Standards per NCI – CTEP:

- Unrelated: The Adverse Event is clearly not related to the investigational agent(s)
- Unlikely: The Adverse Event is doubtfully related to the investigational agent(s)
- Possible: The Adverse Event may be related to the investigational agent(s)
- Probable: The Adverse Event is likely related to the investigational agent(s)
- Definite: The Adverse Event is clearly related to the investigational agent(s)

## **14. YALE PRINCIPAL INVESTIGATOR SAE REPORTING REQUIREMENTS**

### **14.1 Expedited Reporting of Unexpected SAEs**

AEs classified as “serious” and “unexpected” that are possibly, probably, or definitely attributed to drug administration, or SAEs whose frequency exceeds expectations, require expeditious handling and reporting.

The PI will promptly investigate all safety information related to an adverse experience. If the results of the PI’s investigation show an adverse drug experience not initially determined to be reportable (based on whether the event is serious, unexpected, and associated with drug administration) is so reportable, the PI will report such experience. Follow-up information to a safety report shall be submitted as soon as the relevant information is available.

#### Reporting to the Yale Human Investigation Committee

All SAEs, whether originating at Yale or a collaborating center, meeting the criteria for expedited reporting will be reported to the Yale University Human Investigation Committee (HIC) using HIC Form 6A within 48 hours of discovery.

The Yale University Human Investigation Committee expedited reporting criteria are:

- a. Serious AND unanticipated AND possibly, probably or definitely related events; and
- b. Anticipated Adverse Events occurring with a greater frequency than expected.

The HIC does not require reporting of any other Adverse Event type. A copy of the HIC Adverse Event Policy is available at: <http://info.med.yale.edu/hic/policy/AdverseEventPolicy.pdf>

### **14.2 Duration of Reporting of SAEs**

From the date of first treatment until 30 days (unless otherwise specified) subsequent to last treatment or withdrawal of subject, new onset adverse events will be captured. Follow-up and reporting of these events will follow the same procedure as for AEs observed during the study period. In addition, any unexpected Serious Adverse Event that occurs more than 30 days after drug administration but is possibly, probably or definitely attributed to drug administration will be recorded and reported.

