### 2.2 Secondary Objectives

- 2.2.1 To evaluate the radiographic response to neoadjuvant therapy by comparing IV contrast CT scans before and after therapy.
- 2.2.2 To evaluate the pathologic response to neoadjuvant chemotherapy and stereotactic radiation.
- 2.2.3 To determine rates of recurrence (local only, systemic only, and both local and systemic), progression free survival, and overall survival.
- 2.2.4 To determine rates of grade 3 or greater gastrointestinal toxicity, including acute toxicities occurring within 3 months of treatment, and late toxicities occurring over 3 months after completion of radiation.

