### **4.3 Radiation-Specific Safety Guidelines**

The radiation fractionation scheme proposed in this study (33 Gy in 5 fractions) was evaluated in a prospective multi-institutional phase II study in which patients with locally advanced pancreatic cancer received gemcitabine followed by SBRT. The rate of grade 3 or higher acute GI toxicity was 2% and the rate of grade 3 or higher late GI toxicity was 8%. Based upon this study and other published studies evaluating multi-fraction SBRT for pancreatic cancer, a rate of grade 3 GI toxicity of 20% or higher would be unexpected. An interim safety analysis will be performed by the PI after 5 patients complete 3 months of follow-up after SBRT. Study accrual will continue during this time period. If the rate of grade 3 GI toxicity that is probably related to SBRT exceeds 20%, then accrual will be held and the protocol and consent will be revised.

Refer to section 7 for recommendations for the management of toxicities related to SBRT.

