#### **6.3 Surgery**

After completion of SBRT, patients will undergo re-evaluation for resection with a pancreas protocol CT scan, MRI if CT scan can not be tolerated, and PET or EUS if deemed necessary to determine resectability. Those patients who are determined to be potentially resectable will undergo a laparoscopy, followed by surgical resection within 4-12 weeks after completion of SBRT. For surgical resections occurring more than 12 weeks after SBRT, exceptions will be recorded and patients can remain on study with PI approval. Standard pathologic evaluation and staging will be performed.

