Secondary endpoints include radiographic response to neoadjuvant therapy, pathologic response to neoadjuvant therapy, rates of recurrence (local only, systemic only, and both local and systemic), progression free survival, overall survival, and rates of grade 3 or greater acute and late gastrointestinal toxicity. We will compare levels of KRAS mutation-associated circulating tumor DNA, CA19-9, and elastography measures with outcomes including R0 resection using logistic regression, and progression free survival and overall survival using proportional hazards regression. We will code IV contrast scans as binary and compare the before/after treatment within the same subject using the McNemar test for matched pairs. We have not powered this study for these secondary and exploratory measures. Future correlative biomarker studies will be studied using standard bioinformatics methods. Progression free survival, and overall survival will be estimated using Kaplan-Meier analysis. The Cox proportional hazards regression model will be used to determine if survival outcomes are associated with patient characteristics or treatment-related toxicities.

We anticipate accrual will be completed in two years based on the fact that approximately 40 resections for pancreatic adenocarcinoma are performed annually at Yale New Haven Hospital, of which around a third are for BRPC.

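### Late grade 3 or higher GI toxicity after SBRT is a secondary endpoint, but adverse event capture and the visit calendar barely reach the late period, so late events would be under-counted

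*Combined protocol and SAP*

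**What the plan says.** Section 2.2 (objective 2.2.4) includes "late toxicities occurring over 3 months after completion of radiation", with no upper time limit. Section 3.3.2 lists the same outcome, and Section 12 names "rates of grade 3 or greater acute and late gastrointestinal toxicity" among the secondary endpoints.

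The collection rules are in Sections 13.1 and 14.2. Section 13.1 sets a minimum: "The evaluation period should extend from date of first treatment until at least 30 days (or longer if so specified) from the last dose". As its alternative finishing point, the same sentence lets safety evaluation run on "until resolution from all acute toxicities associated with the drug administration". Section 14.2: "From the date of first treatment until 30 days (unless otherwise specified) subsequent to last treatment or withdrawal of subject, new onset adverse events" are captured. Beyond 30 days, Section 14.2 adds only "any unexpected Serious Adverse Event that occurs more than 30 days after drug administration but is possibly, probably or definitely attributed to drug administration".

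In the Section 8 calendar, the Toxicity Assessment row is marked at screening, on day 1 of each neoadjuvant and adjuvant cycle, and weekly during SBRT. It is blank in the pre-operative, post-treatment and 30-day columns and does not appear in the long-term tables.

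Section 10 admits to surveillance only patients who finish study treatment without progression. For all other patients the only follow-up it states is for survival.

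**The concern.** The endpoint begins about 13 weeks after SBRT, whereas the capture rule is tied to the last treatment and runs 30 days past it. For a patient whose last treatment is SBRT, the window closes before the late period opens. The provision for events after 30 days does not fill the gap. It is limited to unexpected events attributed to drug, while late GI toxicity is expected after SBRT (Section 4.3 cites 8% at grade 3 or higher) and is a radiation effect.

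If late time that nobody observed is treated as event-free, the reported late rate is too low. Observation time also depends on outcome: patients found unresectable, progressing or withdrawn are watched for the shortest time. Section 12 plans Cox models relating survival to treatment-related toxicities, so unequal observation could distort that analysis too.

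The reference study in Section 4.3 reports 2% acute and 8% late grade 3 or higher GI toxicity. On those figures most of the severe GI toxicity expected from SBRT falls in the poorly observed period.

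**Working it through.** The plan gives no figure for late coverage, so there is none to reproduce. The check is timeline arithmetic in weeks from completion of SBRT.

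**Inputs**
- Late period starts at 3 months, about 13 weeks (objective 2.2.4).
- Capture ends 30 days after last treatment or withdrawal: 30/7 = 4.3 weeks (Section 14.2).
- SBRT to surgery: "surgical resection within 4-12 weeks after completion of SBRT" (Section 6.3).
- Surgery to adjuvant start: 0 to 12 weeks (Section 6.4 sets only the upper limit).
- Four adjuvant cycles at two-week intervals: day 1 of cycle 4 falls 6 weeks after day 1 of cycle 1 (Sections 6.1 and 6.4).
- Withdrawal without adjuvant therapy is assumed to fall in the same 4 to 12 weeks as surgery.

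**Formulas**
- End of capture = time of last treatment or withdrawal + 4.3.
- Late coverage = end of capture − 13, or 0 if negative.

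| Route | Capture closes (weeks) | Late weeks covered |
|---|---|---|
| SBRT is the last treatment | 0 + 4.3 = 4.3 | 0 |
| No adjuvant therapy, clock from surgery or withdrawal | 4 + 4.3 = 8.3 to 12 + 4.3 = 16.3 | 0 to 3.3 |
| Four adjuvant cycles completed | 4 + 0 + 6 + 4.3 = 14.3 to 12 + 12 + 6 + 4.3 = 34.3 | 1.3 to 21.3 |

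The best case, 21.3 weeks, is just under 5 months.

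**First scheduled Toxicity Assessment after the last SBRT week.** This is adjuvant day 1: 4 + 0 = 4 weeks to 12 + 12 = 24 weeks. A patient who receives SBRT but no adjuvant therapy has none.

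**Share of late time covered.** The plan gives no horizon, so two are assumed.
- To 1 year (52 − 13 = 39 late weeks): without adjuvant therapy 0 to 3.3/39 = 8%; with it 1.3/39 = 3% to 21.3/39 = 55%.
- To 3 years (156 − 13 = 143 late weeks): without adjuvant therapy 0 to 3.3/143 = 2%; with it 1.3/143 = 1% to 21.3/143 = 15%.

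These are shares of time, not of events, because the documents give no onset distribution.

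**Scale of the endpoint.** If all 28 patients received SBRT and the cited 8% applied, 28 × 0.08 = 2.24 late events would be expected. Missing one or two would change the reported result.

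**Does any text specify a longer period?**
- Objective 2.2.4 defines the endpoint but sets no collection period.
- Section 4.3 comes closest: "An interim safety analysis will be performed by the PI after 5 patients complete 3 months of follow-up after SBRT". That follow-up ends where the late period begins.
- The open-ended clause in Section 13.1 is confined to acute toxicities of drug administration.

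**The case against.** The best defence is that the 30 days is a minimum which yields to other text, and that other text exists. Section 13.1 calls for a focused history and evaluation of any sign of treatment-related toxicity at each visit. Section 13.3 requires CTCAE grading without a time limit. Surveillance brings patients in every 3 months for 3 years with history, physical examination and laboratory tests, and Section 6.4 adds two-weekly contact after surgery. Sections 14.1 and 14.2 govern reporting rather than collection of a secondary endpoint, and Section 14.1 also covers anticipated events that exceed their expected frequency. The endpoint is unpowered and does not affect the primary decision. Section 12 states no denominator, so counting unobserved time as event-free is an inference.

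Part of this stands. Late coverage is not zero, late visits do exist, and a broad reading of Section 13.1 would recover some events in patients under surveillance. The 1.3-week figure assumes adjuvant therapy starts on the day of surgery, so it is a bound and not a typical case; a 4-week gap gives 4 + 4 + 6 + 4.3 − 13 = 5.3 weeks. The direction of bias does depend on how the rate is formed, which the plan leaves open.

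The rest does not close the gap. A focused history neither extends the capture period nor puts a toxicity item on the calendar, and grading applies only to events that someone records. The excess-frequency rule likewise needs the events to be captured first. Extending capture to the 3 months in Section 4.3 adds no late time. None of these provisions reaches patients who leave after SBRT and have only survival follow-up.

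**Conclusion.** The concern holds. Followed as written, the capture rule and calendar observe 0 to about 3 weeks of the late period in patients without adjuvant therapy, and about 1 to 21 weeks in those who complete it. Late grade 3 or higher GI events would tend to be under-counted, and ascertainment would be poorest in patients who stop early.

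The windows rest on the protocol's stated intervals; surgery approved beyond 12 weeks or delayed chemotherapy would lengthen them. The percentage shares rest on assumed 1-year and 3-year horizons. The downward direction assumes that the rate is taken over treated patients without allowing for unobserved time. The size of the bias cannot be estimated, because neither onset timing nor a horizon is given. The primary endpoint is unaffected, but a low late-toxicity rate could not be told apart from lack of observation, so the plan should be amended.

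**What to change.** 1. **Calendar (Section 8).** Add a GI toxicity item recording grade, onset date and attribution to SBRT at the pre-operative, 30-day, post-treatment and long-term visits already scheduled.
2. **Patients off treatment early (Section 10).** Add a GI toxicity question to the survival contact for anyone who received SBRT but does not enter surveillance.
3. **Capture period (Sections 13.1 and 14.2).** State that grade 3 or higher GI events are captured throughout follow-up for everyone who received any SBRT, and refer to protocol treatment (drug, SBRT or surgery) instead of drug administration alone.
4. **Analysis (Section 12).** Report the late rate among SBRT-treated patients followed beyond 3 months, for example as a cumulative incidence, with the number at risk.

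The cost is one amendment, one extra case report form item at visits that mostly include a history and physical examination already, and one question at survival contacts. Only data collection and reporting change; treatment does not.

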## **15. YALE SAFETY REPORTING AND MONITORING (DSMP)**

The principal investigator at the Yale Cancer Center will monitor the clinical trial for safety. The principal investigator will assess all expedited adverse events and will periodically review all adverse events observed on the trial. Yale Cancer Center standard operating procedures (SOPs) for assessment and reporting of adverse events are followed which are in compliance with FDA 21 Code of Federal Regulations Part 312.32 and 312.33.

The clinical trial data consisting of all required observations, AEs, and laboratory data will be entered into a computerized database (OnCore) in a timely manner. The accuracy and completeness of the database, timely submission of SAEs and compliance with the protocol, is assured by periodic auditing conducted by the Yale Cancer Center Office of Protocol Review and Monitoring, which reports to the

Yale Data and Safety Monitoring Committee (DSMC). Safety data will be submitted to DSMC at least once yearly or more often as required by the DSMC. On a regular interval basis, status reports of all laboratory parameters, AEs and SAEs are reviewed by the PI to view composite data across subjects. Regular meetings are held to discuss ongoing patient treatment and adverse events.

The Yale DSMC will perform an interim safety analysis after enrollment of 10 patients to determine whether there are any safety issues and to assess whether it is safe to continue enrollment. Enrollment will be suspended until approval is granted from the DSMC to proceed completion of enrollment.

Possible actions taken by the PI or the Yale DSMC if a new unexpected toxicity is identified from the above safety review, or if the periodic review of all adverse events and laboratory data indicates a pattern of incidence or severity of toxicity that raises a safety concern, can be to:

- Revise consent form
- Amend the protocol
- Suspend the protocol

All AEs found to be expected or non-serious, will be included in the Annual Report.

## **16. RETENTION OF RECORDS**

U.S. FDA regulations (21 CFR 312.62[c]) require that records and documents pertaining to the conduct of this study and the distribution of investigational drug, including CRFs, consent forms, laboratory test results, and medication inventory records, must be retained by the principal investigator for 2 years after the investigation is discontinued.

## **17. RESEARCH ETHINCS AND HUMAN SUBJECT PROTECTION**

### **17.1 Subject Selection**

This protocol will seek to accrue patients 18 years of age or older as described in the study inclusion criteria.

### **17.2 Informed Consent Process**

The informed consent dialogue with the research subjects will include a discussion of the natural history of their condition and alternative therapies that a person might consider (e.g. supportive care only, administration of conventional chemotherapy agents, or participation in a research study).

### **17.3 Confidentiality**

Data collected on each patient will be maintained in a research folder kept in a locked room. Data entered into a computerized database will be kept on a computer that is password protected and kept in a locked room. In all publications and presentations resulting from this research project, the research subject's anonymity will be protected to the maximum extent possible. Authorized Medical Department personnel and personnel from the cancer center and IRB may have access to their research file in order to verify that the research subject's rights have been safeguarded. In addition, their name will be given

to the Clinical Studies Unit, a contracting office who will register the research subject onto this study and verify their eligibility.

